11.1.4 Safety Measures during the PUSH Intervention

The PUSH intervention will be conducted in the participant's place of residence and all sessions will be conducted and supervised by trained PTs, who monitor potential adverse experiences and symptoms. PTs will be trained to deal with medical emergencies that occur during the PUSH sessions and will be CPR certified. Also, community EMS services will be activated if needed.

In order to minimize discomfort and maximize safety, participants will be taught the proper method for performing each exercise and the importance of following the proper method. Intensity is gradually increased, and exercise technique is commented on during each session. Participants will be instructed to talk with the PTs about any muscle soreness, pain or discomfort.

Every effort will be made to prevent harm by stopping intervention activity when the participant reports chest pain, dizziness, significant shortness of breath, or severe musculoskeletal pain. PTs will monitor blood pressure at the start of the training session, mid-session, and when participants are finished with the session. Blood pressure and heart rate will be monitored using a standard blood pressure cuff and palpation of peripheral pulse. If blood pressure is elevated above 170/100, the participant will rest quietly for a few minutes. The PT will monitor the participant for signs of muscle strain, dizziness, or hypotension and appropriate palliative methods will be discussed with the participants and appropriate medical referrals will be made. Please see Table 3 for a summary of alerts and appropriate action during the PT intervention visits.

11.1.5 Safety Considerations for the Protein Intervention

Although the protein supplement used in this study is virtually lactose (sugar) free, small amounts of lactose may trigger digestive upset (abdominal pain, gas, and diarrhea) for participants who suffer from lactose intolerance. Although this product may not contain one or all of the following, this product is manufactured in a facility that handles milk, soy, egg, peanut, nut, tree, fish, crustaceans/shellfish, and wheat products. Those who have celiac disease or who have a known allergy to dairy, peanuts, or shellfish are excluded from participation. Whey provides no fiber to the diet, and excessive consumption may lead participants to experience constipation unless they consume high-fiber foods in addition to whey. There is an extremely low risk of renal (kidney) or liver damage related to whey protein supplementation. Those with a history of severe liver disease (e.g., hepatitis, fatty liver disease, cirrhosis), chronic kidney disease (CKD stage 4), or a calculated creatinine clearance 15-29 ml/min are excluded from participation. There is an extremely low risk that participants with poorly controlled type 2 diabetes could experience hypoglycemia (low blood sugar). Those with hemoglobin A1c level greater than 10% are excluded from participation. Please see Table 3 for a summary of alerts and appropriate action for the protein intervention.

Table 3. Safety Alerts and Actions for Interventions

ALERT	ACTION
Resting blood pressure SBP > 170mm Hg or SBP < 90mm Hg or DBP > 100mm Hg or DBP < 50mm Hg	
 1. If initial BP check is high (systolic > 170; diastolic >100), have participant sit for 5 minutes and rest then check BP again. This may be done twice. 2. If three BP readings are greater than 170/100, then individual should not exercise. 3. The PCP, study coordinator, and study physician should be called before exercise is initiated. 4. If initial BP is low for that person (systolic<90; diastolic<50) follow same protocol.
New chest pain	Call 911.
Reported chest pain that occurred between visits	
 1. Cancel treatment and call PCP. 2. Report to study coordinator and study physician to follow-up until cleared.
Acute shortness of breath	
 1. Have participant stop exercising and rest. 2. Take vital signs. 3. If the shortness of breath does not resolve itself in 10 minutes, and vital signs are not within normal limits for participant, call 911. 4. Report to PCP, study coordinator, and study physician.
Fall	
 1. If there is bleeding/wound, apply pressure using emergency kit for wound; call 911 if needed. If participant is unable to stand or move the injured part, call 911 and keep them warm and comfortable. 2. Report all falls to study coordinator. 3. Complete an incident report.
Stroke symptoms	Call 911 immediately.
Dizziness during exercise	
 1. Stop exercise and have person sit or lie down. 2. If sitting is not sufficient to resolve dizziness, then check vital signs. 3. Call 911 if clinically unstable. 4. Report to PCP if heart rate is less than 60 (and not usually so), the dizziness is new in onset; or if the BP is > 160/100 or systolic <90. 5. Report event to study coordinator and study physician.

ALERT	ACTION
Resting pulse Rate > 120 or < 40 beats/min	
 1. PT will stop delivery of the intervention. 2. Qualified staff will consult with the study physician and follow up as needed. 3. PT will resume delivery of the intervention only after the participant receives medical clearance.
New irregular heart rate with complaint of heart palpitations	
 1. Do not exercise and call PCP. 2. Report to study coordinator and study physician for follow-up. 3. Wait for medical clearance to resume exercise.
New acute musculoskeletal pain during exercise (pain > 5 on VAS)	
 1. Have the participant stop the exercise and rest. 2. Attempt to alter position of participant to reduce pain. If pain persists, do not continue specific exercise. Attempt to do other exercises. 3. If pain does not resolve, refer to PCP or orthopedist and study physician.
New, acute, non-musculoskeletal pain (pain > 5 on VAS)	
 1. Do not exercise. 2. Take pain history and call PCP. 3. Report to study coordinator and study physician for follow-up and clearance.
Acute change in mental status	
 1. Do not exercise. 2. Call PCP or if unavailable, call 911. 3. Report to study coordinator and study physician for follow-up and clearance.
Participant expresses desire to commit suicide	
 1. Call PCP and report findings. 2. Report to study coordinator and study physician for follow-up and clearance.
Participant exhibits signs of allergic reaction to protein.	
 1. Do not give protein supplement. 2. Call PCP and report findings. 3. Report to study coordinator and study physician for follow-up and clearance.

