9.6.4 Expected Adverse Events (AEs)

Expected AEs will be assessed every four weeks during the telephone interview. Participants (or their proxies) will be asked a series of standardized questions related to pain (feet, hip, back, knees, digestive and stomach); breathing problems or chest pain; bloating or puffiness in legs, ankles, or feet; drowsiness, dizziness, or confusion; shakiness, anxiety, clammy skin, or irritability; and falls (with and without injury).

Section 10: Study Procedures

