11.1.7 Safety Considerations for Nutritional Support

Individuals who have sustained a hip fracture are frequently at risk for protein and calorie malnutrition and have low calcium and vitamin D intake.¹⁶⁸ Individuals enrolled in the study will be screened with the MNA®-SF and if their scores indicate that they are malnourished, they will receive in-person nutritional counseling by a registered dietitian. Individuals enrolled that have a serum albumin value 2.5-3.5 will also receive in-person nutritional counseling by a registered dietitian, regardless of score on the MNA®-SF. Participants who are at risk or not at risk for malnutrition will receive a telephone consultation from the dietitian on maintaining proper diet.

The RD will schedule an in-person visit for those at risk if he/she feels it is necessary based on the telephone consultation. All subjects will receive vitamin D, calcium, and multivitamin supplementation for the 16-week study period, all of which represent best practices for this disabled group of participants. There are small risks associated with vitamin D, calcium, and multivitamins including gastrointestinal complaints (including mild constipation or diarrhea, stomach upset) and kidney stones. Those with a calculated creatinine clearance less than 30 ml/min, elevated total or ionized calcium, or history of kidney stones, primary hyperparathyroidism, or sarcoidosis will not receive calcium supplements. A participant who experiences an episode of kidney stones during the study period will stop receiving calcium supplements.

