12.3 Expected AEs

Expected AEs will be captured through telephone interviews every four using the Expected Adverse Events Form. Following are expected adverse events that have been listed in the ICF:

- foot pain
- hip pain
- back pain
- knee pain
- digestive or stomach pain
- breathing problems
- chest pain or discomfort
- bloating or puffiness in the legs, ankles, or feet
- drowsiness, dizziness, or confusion
- shakiness, anxiety, clammy skin, or irritability
- fall (with or without injury)

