12.4.2 Unexpected Adverse Event

Unexpected AEs will be defined as medical events that occur during study participation, but do not commonly occur in the study population and which are not listed in the ICF or study protocol (section 12.3). An unexpected AE may be witnessed by a member of the research team, or staff may be told about an unexpected event that may meet the criteria for reporting.

Unexpected AEs that have a potential relationship to study procedures and activities will be captured on an Incident Report and submitted to the study office where they will be logged in the participant binder and then reported to the Independent Safety Monitor (ISM).

A reportable unexpected AE will be one that meets all of the following criteria:

- Unexpected, in terms of nature, severity, or frequency, given (a) the research procedures that are described in the protocol-related documents, such as the IRB-approved research protocol and ICF; and (b) the characteristics of the study population;
- Related or possibly related to participation in the research (meaning that there is a reasonable possibility that the incident, experience, or outcome may have been caused by the procedures involved in the research);
- Suggests that the research places participants or others at a greater risk of harm (including physical, psychological, economic, or social harm) than was previously known or recognized.

The medical and scientific judgment of the study physician and the PI will be exercised in deciding whether an occurrence should be reported. In addition, difficulty determining whether or not an event is unexpected and/or attributable to the intervention will be addressed by the ISM, who will determine if the event is to be reported.

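### Gas, diarrhoea and constipation are named as possible effects of the study products but are not asked about, so digestive tolerability will be under-counted

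*Protocol*

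**What the plan says.** **Risks named.** Protocol 11.1.5 says of the whey powder that "small amounts of lactose may trigger digestive upset (abdominal pain, gas, and diarrhea"), for participants who are lactose intolerant. It adds that "excessive consumption may lead participants to experience constipation unless they consume high-fiber foods in addition to whey". Section 11.1.7 attributes to vitamin D, calcium and the multivitamin small risks that include "gastrointestinal complaints (including mild constipation or diarrhea, stomach upset").

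**Symptoms asked about.** Section 9.6.4 describes the standardised questions put at each four-weekly call. They cover "pain (feet, hip, back, knees, digestive and stomach"), then breathing problems or chest pain, "bloating or puffiness in legs, ankles, or feet", two groups of general symptoms, and falls.

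**Events listed as expected.** Section 12.3 introduces its list with "Following are expected adverse events that have been listed in the ICF". The only digestive entry among its 11 items is "digestive or stomach pain".

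**Objective served.** Sections 1 and 4.2 make the safety and tolerability of delivering PUSH Plus Protein a study objective. Neither protocol section 14 nor the SAP defines a tolerability endpoint or an analysis for it.

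**The concern.** The protocol predicts certain digestive symptoms in one place and does not ask about them in another. Relying on participants to volunteer mild symptoms generally yields fewer reports than asking directly, so the plan as written should under-count gas, diarrhoea and constipation.

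This matters for three reasons. First, protein is the component whose addition the pilot is testing against PUSH alone, and its tolerability is one of the things a definitive trial would take from this study. Second, lactose-intolerant people can enrol: section 7.3 excludes known dairy allergy and celiac disease but not lactose intolerance. The group that 11.1.5 describes as susceptible may therefore take the powder daily for 16 weeks. Third, section 12.8 has the DSMB review non-serious and expected events for rates higher than anticipated. It cannot do that dependably for symptoms that are not collected systematically.

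**Working it through.** The plan gives no figure on this point, so the check is a match of named risks against collected symptoms.

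| Symptom named | Where named | Solicited in 9.6.4 | Listed in 12.3 |
|---|---|---|---|
| Abdominal pain | 11.1.5 (whey) | Yes, as digestive and stomach pain | Yes |
| Gas | 11.1.5 (whey) | No | No |
| Diarrhoea | 11.1.5 (whey), 11.1.7 (supplements) | No | No |
| Constipation | 11.1.5 (whey), 11.1.7 (supplements) | No | No |
| Stomach upset | 11.1.7 (supplements) | Only if reported as pain | Only if reported as pain |

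*Count for whey.* Four gastrointestinal effects are named and one is covered, so 4 − 1 = 3 are neither solicited nor listed.

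*The bloating item does not fill the gap.* It is confined to the legs, ankles and feet, so it concerns limb swelling and not abdominal gas.

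*Other content of the calls.* Section 10.3 lists three things: the reportable-event form, the expected-event form, and self-reported adherence to protein and supplements. Over 16 weeks at four-week intervals that is 16 / 4 = 4 calls per participant, none with an item for these symptoms.

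*Reportable-event stream.* Section 12.4 restricts this to serious events, unexpected events and injuries under supervision. Ordinary gas, diarrhoea or constipation would not normally qualify. A reportable unexpected event must meet all three criteria in 12.4.2, including that it suggests a greater risk than was previously known, and these risks are already stated in section 11.

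*Adherence data.* Section 9.6.1 records the reason for each missed therapy visit. For protein it specifies only container weight and self-report, with no reason for non-use. Low intake would be visible, but it could not be traced systematically to digestive intolerance.

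*Balance of the items.* Section 11.1.5 calls the risk of hypoglycaemia extremely low, yet symptoms that fit it (shakiness, clammy skin) are asked about. Gas, diarrhoea and constipation carry no such qualifier and are not asked about.

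**The case against.** The strongest reply is that the plan has other ways to learn of these symptoms. Section 11.3 instructs participants to report adverse events at scheduled contacts, to the therapists, or at any other time. Therapists make up to 32 home visits, and 11.1.4 has them monitor for adverse experiences and symptoms. Section 11.1.6 promises monitoring for adverse events with the protein. Container weights and self-report would show participants who stop taking it. Abdominal pain, the first symptom in the lactose warning, is asked about. All of this stands, and it limits the point to under-ascertainment. It does not remove the point, because these routes either rely on volunteering or name no form for a mild, known, unlisted symptom.

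A reader might go further and infer three things that the documents do not support.

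- *That volunteered events would be misclassified as unexpected.* Section 12.4.2 does refer to events "which are not listed in the ICF or study protocol (section 12.3"), but it also requires that the event not commonly occur in the study population. Section 12.2.2 lets the independent safety monitor class an event as expected if it was anticipated from prior experience with the intervention or is attributable to the patient population. Absence from the list is not enough to make an event unexpected.
- *That the supplement's main side effects are missed.* The protocol gives no ranking. It describes the product as virtually lactose free and ties lactose upset to intolerance and constipation to excessive consumption.
- *That the study would report none in 30.* This assumes that nobody volunteers anything over 16 weeks, and the documents give no incidence from which to project a count.

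It is also fair to object that the consent form and the event forms are not among the documents. The finding rests on the protocol's description of what they contain.

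**Conclusion.** The concern holds in a limited form. Three of the four gastrointestinal effects that the protocol names for whey, two of which it also names for the vitamin and calcium supplements, are neither solicited nor listed as expected. Digestive tolerability is under-ascertained: the direction of the error is towards too few events, and its size cannot be stated from the documents.

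This rests on two assumptions. One is that the Expected Adverse Events Form follows the topics in 9.6.4 and 12.3. The other is that symptoms not asked about are recorded less completely than symptoms that are. The gap bears on the tolerability objective and the DSMB's tabulations, not on the walking-distance comparison.

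**What to change.** Add three separate items, gas/abdominal bloating, diarrhoea and constipation, to the Expected Adverse Events Form used at the four-weekly calls. Make the same additions to the topics in 9.6.4, the list in 12.3 and the matching list in the consent form. Report the proportion of participants with each symptom, with an exact binomial interval. The denominator should be those actually asked.

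State alongside the results that this is a single arm taking whey, vitamin D, calcium (unless contraindicated) and a multivitamin together. The rates describe the combined regimen and cannot be attributed to whey alone.

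The cost is a form revision and an IRB amendment, slightly longer calls, and missing early items for anyone already enrolled when the form changes. Symptoms not asked about at those early calls cannot be reliably recovered later, so the change is worth more the sooner it is made.

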11.1.6 Safety Measures for the Protein Intervention

In order to minimize discomfort and maximize safety, PTs will instruct participants on how to take the protein supplement. We will monitor for potential adverse events. A participant who exhibits signs of allergic reaction to the protein will stop receiving the protein supplement and the study physician and PCP will be consulted.

11.1.7 Safety Considerations for Nutritional Support

Individuals who have sustained a hip fracture are frequently at risk for protein and calorie malnutrition and have low calcium and vitamin D intake.¹⁶⁸ Individuals enrolled in the study will be screened with the MNA®-SF and if their scores indicate that they are malnourished, they will receive in-person nutritional counseling by a registered dietitian. Individuals enrolled that have a serum albumin value 2.5-3.5 will also receive in-person nutritional counseling by a registered dietitian, regardless of score on the MNA®-SF. Participants who are at risk or not at risk for malnutrition will receive a telephone consultation from the dietitian on maintaining proper diet.

The RD will schedule an in-person visit for those at risk if he/she feels it is necessary based on the telephone consultation. All subjects will receive vitamin D, calcium, and multivitamin supplementation for the 16-week study period, all of which represent best practices for this disabled group of participants. There are small risks associated with vitamin D, calcium, and multivitamins including gastrointestinal complaints (including mild constipation or diarrhea, stomach upset) and kidney stones. Those with a calculated creatinine clearance less than 30 ml/min, elevated total or ionized calcium, or history of kidney stones, primary hyperparathyroidism, or sarcoidosis will not receive calcium supplements. A participant who experiences an episode of kidney stones during the study period will stop receiving calcium supplements.

11.1.8 Safety Measures for Nutritional Support

If a participant loses 2% or more body weight in a four-week period, the participant will be referred to the registered dietician for follow-up by telephone.

11.2 Confidentiality

Confidentiality of data will be maintained by using research identification numbers and letter codes that uniquely identify each individual. Safeguards will be established to ensure the security and privacy of participants' study records. Data will be stored in locked files and on computer disks, with access limited to the investigators and key study personnel. Computer data files will not include participant names, addresses, initials, hospital record number, or any other personal identifiers. Computer security procedures, including multiple levels of password protection will be instituted. Data for publication will be presented only in aggregate form, preventing identification of individual participants. After the study is completed, local data will be archived in a secured storage area.

In compliance with the Health Insurance Portability and Accountability Act (HIPAA) and the Standards for Privacy of Individually Identifiable Health Information of the Department of Health and Human Services, CAP will access personal health information and medical records only after receiving approval for a HIPAA Partial Privacy Waiver for Recruitment. Only information necessary for determining eligibility will be obtained.

11.3 Participant Education about Potential Risks

Potential risks associated with study-related activities and interventions will be explained to each participant by trained study personnel during the informed consent process. Each participant will be instructed to report the occurrence of an AE to appropriate study staff at scheduled data collection times, to PTs administering the intervention, or spontaneously at any other time. Participants also will be encouraged to report concerns about the safety of participating in the study.

Section 12: Reportable Adverse Events (RAEs) and Expected Adverse Events (AEs)

12.1 Overview

In this study we will capture study-defined expected adverse events (AEs) through structured telephone interviews every four weeks. Reportable AEs (RAEs) are defined as serious adverse events (SAEs), AEs that have potential implications for participant safety, unexpected AEs, and injury that occurs while a participant is under the supervision of study related personnel. These

RAEs will require individual event reporting as described in section 12.4. The timely and complete account of RAEs will be a critical requirement for the protection of human subjects in this study.

The University of Maryland Claude D. Pepper Older American Independence Center (UM-OAIC) DSMB will review and approve study-defined expected AEs and will be involved in regular monitoring of the RAE reporting system.

12.2 Classifying Adverse Events

An AE is any unfavorable or unintended medical occurrence in a human study participant that has taken place during the course of a research project, including any abnormal sign, symptom, or disease, whether or not related to participation in the research

For the purposes of this study, any event that meets the criteria for an SAE, is unexpected, or results in injury to the participant while s/he is under the supervision of study related personnel will be classified as an RAE.

Adequate review, assessment, and monitoring of RAEs require that they be classified as to severity, expectedness, and potential relatedness to the study intervention.

